SI	Site Investigator
SMC	Safety Monitoring Committee
SOP	Standard Operating Procedure
SVC	Slow Vital Capacity
Tregs	T regulatory cells
US	United States
VC	Vital Capacity
WOCBP	Women of Childbearing Potential

PROTOCOL SUMMARY

Study Title

A PILOT STUDY OF RNS60 IN ALS

Version Number

6.0

Protocol Number

RNS60-01

Study Indication

Amyotrophic Lateral Sclerosis (ALS)

[figure not shown]
Phase of Development

IIa

Rationale for the Study

Amyotrophic lateral sclerosis (ALS) is a fatal, neurodegenerative disease for which there is no cure.

A substantial body of evidence implicates the neuroimmune system and specifically activated microglia in ALS pathophysiology. Activated microglia are increased in postmortem brain and spinal cord tissue from patients with ALS compared to healthy controls, and the number of activated microglia correlates positively with faster rate of disease progression. In addition, studies of blood cells in people with ALS have shown an increased activation of two of the major inflammatory cell types in the body, monocytes and T cells. Among T cells, regulatory T cells (Tregs) have been recently proposed to play a role in ALS progression. Tregs and their FoxP3 protein expressions were reduced in rapidly progressing ALS patients and inversely correlated with progression rates. A 3.5-year prospective study revealed that early reduced FoxP3 levels were predictive of future rapid progression and attenuated survival. These data suggest that Tregs may influence disease progression rates in ALS.

[REDACTED]

[REDACTED]

[REDACTED]

Study Design

This is a single center, open label, pilot trial of RNS60 in people with ALS. Study participants will receive study drug for 24 weeks following the core study schedule of activities. Upon nearing completion of the core study, subjects will be given the option to continue to receive drug for approximately an additional 24 weeks, for a total of approximately 48 weeks on study drug, following the optional extension phase schedule of activities.

Study Objectives and Endpoints

The primary objectives of the study are to determine the preliminary safety and tolerability of RNS60 treatment in 18 people with ALS over 24 weeks. We will measure the impact of RNS60 on blood biomarkers of inflammation. In addition, in a subgroup of 13 study participants (“Imaging group”), an additional primary objective is to measure the impact of RNS60 on [¹¹C]-PBR28 uptake in the motor cortices and brain stem measured by positron emission tomography (PET) imaging.

RNS60 in ALS

V6.0

5/5/2016

We will also measure the effect of RNS60 on ALS clinical outcomes [ALS functional rating scale (ALSFRS-R), slow vital capacity (SVC), strength (measured by ATLIS- Accurate Test of Limb Isometric Strength)].

For participants who elect to continue with the optional 24 week extension, safety parameters (labs, EKG, adverse events, C-SSRS) will continue to be monitored. We will also collect ALSFRS-R and SVC outcome measures.

Study Location

Massachusetts General Hospital (MGH)

Number of Planned Subjects

Up to 25 subjects will be screened for the study with the goal of enrolling 18 for treatment. All 18 enrolled subjects will be given an opportunity to sign a consent form addendum during Weeks 18-22 to receive approximately 24 additional weeks of drug treatment.

Study Population

This study will be conducted in subjects who meet the El Escorial criteria of possible, laboratory-supported probable, probable, or definite criteria for a diagnosis of ALS. At screening, eligible subjects must be at least 18 years old and must provide written informed consent prior to screening. Subjects on a stable dose of riluzole and those not taking riluzole, and women of child-bearing age at screening are eligible for inclusion as long as they meet specific protocol requirements. Safety, tolerability, blood biomarkers, and clinical outcomes will be collected on all subjects. In a subgroup of 10 study participants (“Imaging group”) neuro-imaging will be performed. Detailed criteria are described in the body of the protocol.

Treatment Plan

RNS60 will be administered in two ways: by intravenous (IV) infusion one day a week (infusion dose: 375ml, infused over a 40-min period) and by inhalation (the remaining 6 days a week, 4 ml/day) for 24 weeks or up to approximately 48 weeks.

Duration of Treatment and Follow-up

Subjects will remain on treatment in the core study for 24 weeks. Each subject will also have a Week 28 Follow-up Telephone Interview to assess for adverse events (AEs), changes in concomitant medications and to administer the ALSFRS-R. After the completion of the trial, subjects will be called by phone approximately every 3 months to ascertain ALSFRS-R and vital status for up to 2 years.

Optional Extension Phase

Upon nearing completion of the core study, subjects will be given the option to continue RNS60 treatment for an additional 24 weeks of weekly infusions and daily inhalations. Subjects interested in continuing treatment in the extension phase will sign an additional IRB-approved consent addendum document with the physician-investigator during a clinic visit between Week 18 and Week 23. Extension phase drug dispensing will occur at the Week 23 visit. Safety parameters such as blood work, urine samples, EKGs, and adverse event recording will continue to be monitored during the extension phase. ALSFRS-R and SVC outcome measures will be collected at two time points. Each subject will also have a Week 52 Follow-up Telephone Interview to assess for adverse events (AEs), changes in concomitant medications and to administer the ALSFRS-R. After the completion of the trial, subjects will be called by phone approximately every 3 months to ascertain ALSFRS-R and vital status for up to 2 years.

Subjects may choose to discontinue RNS60 treatment at any point during the optional extension phase.

SCHEDULE OF ACTIVITES – CORE STUDY

	Screening Visit ¹	Baseline Visit	Weekly visits Week 1 through Week 10	Wk 11 Visit	Weekly visits Week 12 through Week 22	Week 23 Visit	Week 28 Phone call	Follow Up Chart Review / Phone Call ²	Final Safety Visit (for early study drug discontinuation only) ³
Visit Window	-42 days	Day 0	Day 7 ± 3	Day 77 ± 3	Day 84 ± 3	Day 161 ± 3	Day 196 ± 5	Every 3 months	
Informed Consent	X								
Eligibility Criteria	X	X							
Demographics	X								
ALS History / ALS Diagnosis	X								
Medical History	X								
Blood sample for TSPO Affinity test†	X								
12-lead ECG	X	X				X			X
Safety Labs ⁴	X	X		X		X			X
Vital Signs /Height and weight ⁵	X	X	X	X	X	X			X
Neurological exam	X					X			X
Physical exam	X					X			X
[¹¹ C]PBR28-PET†		X*			X**				
ALSFRS-R		X*		X	X**	X	X	X	X
U Penn Upper Motor Neuron Burden ⁶	X	X		X		X			X
Slow Vital Capacity		X*		X	X**	X		X	X
Strength measurement (ATLIS) ⁷	X	X		X		X			X
C-SSRS		X		X		X			X
RNS60 infusion		X	X	X	X	X			
RNS60 Dispensing (for inhalation)		X	X (week 7)		X (week 15)				
RNS60 Accountability			X	X	X	X			X
AE review ⁸	X	X	X	X	X	X	X		X
Concomitant Meds	X	X	X	X	X	X	X		X
Collection of blood biomarkers		X		X		X			X

¹ Screening procedures must be completed within 6 weeks prior to Baseline Visit.

RNS60 in ALS

V6.0

5/5/2016

² Follow-up will continue every 3 months up to 2 years to collect data on SVC, ALSFRS-R, and survival status. This information may be obtained via chart review and patient contact.

³ Follow-up phone call to occur 28 +5 days after the last dose of study drug if a subject discontinues from the study prematurely.

⁴ Safety labs include Hematology (CBC with differential), Complete Chemistry Panel, Liver Function Tests, Urinalysis, Urine pregnancy test (WOCBP).

⁵ Vital signs include systolic and diastolic pressure in mmHg, respiratory rate/minute, heart rate/minute, temperature and weight. Height measured at Screening Visit only.

⁶ The Penn Upper Motor Neuron-Burden (UMN-B) includes testing of reflexes, the CNS Lability Scale (CNS-LS) and the Ashworth Spasticity Scale.

⁷ If time permits, ATLIS will be performed at the screening visit.

⁸ Adverse events that occur AFTER signing the informed consent form will be recorded.

^{*Off}treatment [¹¹C]PBR28-PET will be performed one time only between the Screening and Baseline visit. ALSFRS-R and SVC will be repeated on the day of the scan.

^{**On}treatment [¹¹C]PBR28-PET will be performed one time only between the Week 18 and Week 23 visits. ALSFRS-R and SVC will be assessed the day of the scan ONLY.

[†]For subjects in the “Imaging group” only.

SCHEDULE OF ACTIVITES – OPTIONAL EXTENSION PHASE

	Weekly visits Week 24 through Week 34	Week 35	Weekly visits Week 36 through Week 46	Week 47	Week 52 Phone Call	Follow Up Chart Review / Phone Call ²	Final Safety Visit (for early study drug discontinuation only) ¹
Visit Window	Day 168 ± 3	Day 245 ± 3	Day 252 ± 3	Day 329 ± 3	Day 364 ± 3	Every 3 months	
12-lead ECG		X		X			X
Safety Labs ³		X		X			X
Vital Signs / Weight ⁴	X	X	X	X			X
Neurological exam				X			X
Physical exam				X			X
ALSFRS-R		X		X	X	X	X
Slow Vital Capacity		X		X		X	X
C-SSRS		X		X			X
RNS60 infusion	X	X	X	X			
RNS60 Dispensing (for inhalation)	X (week 30)		X (week 38)				
RNS60 Accountability	X	X	X	X			X
AE review ³	X	X	X	X	X		X
Concomitant Meds	X	X	X	X	X		X

¹ Follow-up phone call to occur 28 ± 5 days after the last dose of study drug if a subject discontinues from the study prematurely.

² Follow-up will continue every 3 months up to 2 years to collect data on SVC, ALSFRS-R, and survival status. This information may be obtained via chart review and patient contact.

³ Safety labs include Hematology (CBC with differential), Complete Chemistry Panel, Liver Function Tests, Urinalysis, Urine pregnancy test (WOCBP).

⁴ Vital signs include systolic and diastolic pressure in mmHg, respiratory rate/minute, heart rate/minute, temperature and weight.

STUDY WORKFLOW

[figure not shown]
~ 25 Screened

On Active Treatment

Washout Period

18 Subjects on RNS60; drug is administered by weekly IV infusions (infusions to occur at MGH) as well as by intranasal administration the remaining 6 days a week.

6 weeks

Subjects who discontinue from the study early will be asked to return to the study site for Final Safety assessments, and will be asked to have a final Follow-Up Telephone Call 28 days (+5 days) after taking their last dose of study drug.

1 ETHICS/PROTECTION OF HUMAN SUBJECTS

1.1 Institutional Review Board (IRB)

This study will be conducted in compliance with current Good Clinical Practices (GCP) and Title 21 Part 56 of the United States of America Code of Federal Regulations (CFR) relating to IRBs.

1.2 Ethical Conduct of Study

The study will be conducted in accordance with GCP defined by the International Conference on Harmonization (ICH) and the ethical principles of the Declaration of Helsinki.

1.3 Subject Information and Consent

This study will be conducted in compliance with Title 21 Part 50 of the United States of America Code of Federal Regulations (CFR), Federal Regulations and ICH Guidance Documents pertaining to informed consent. At the first visit, prior to initiation of any study-related procedures, subjects will be informed about the nature and purpose of the study, participation/termination conditions, and risks and benefits. Subjects will be given adequate time to ask questions and become familiar with the study prior to providing consent to participate. Subjects will give their written consent to participate in the study and will be provided with a copy of the fully executed consent form for their records.

100% of the time, the system is able to correctly identify the target class.

[figure not shown]
A horizontal bar consisting of three segments: a black segment on the left, a yellow segment in the middle, and a black segment on the right.

Black Box Yellow Box

A large black rectangular redaction box covers the majority of the page content, from approximately y=113 to y=300 and x=113 to x=886.

© 2019 Pearson Education, Inc.

11. **What is the primary purpose of the *Journal of Clinical Endocrinology and Metabolism*?**

[REDACTED]

[REDACTED]

[REDACTED]

[figure not shown]
[REDACTED]

[REDACTED]

1

[REDACTED]

RNS60 in ALS
V 4.0
1/29/2016

3 OBJECTIVES

3.1 Study Objectives

The primary objectives of the study are to determine the safety and tolerability of RNS60 in 18 patients with ALS. The following clinical outcomes will be collected: ALS functional rating scale (ALSFRS-R), slow vital capacity (SVC), strength (measured by ATLIS- Accurate Test of Limb Isometric Strength). An additional primary objective is to measure the impact of RNS60 on several markers of neuro-inflammation measured by blood biomarkers in all subjects and by [¹¹C]-PBR28 positron emission tomography (PET) imaging in a subgroup of 13 subjects.

3.2 Study Outcome Measures

For all subjects enrolled in the study, the following will be primary outcome measures:

- 1- Safety, as measured by AEs and clinically meaningful changes in vital signs, physical examination, and standard clinical laboratory tests;
- 2- Tolerability, defined as the ability of subjects to complete the entire 24-week treatment portion of study;
- 3- Clinical outcomes: Measured by ALSFRS-R, SVC, and strength (measured by ATLIS).
- 4- Blood biomarkers of inflammation.

For subjects in the “Imaging group”, the following additional outcome measures will be obtained:

- 1- Neuroimaging biomarkers ([¹¹C]-PBR28-PET) including both regions of interest (ROI) and voxel-based analyses

4 STUDY DESIGN

4.1 Overall Study Design and Plan

During the enrollment period, approximately 25 subjects will be screened at the Massachusetts General Hospital (MGH). Approximately 18 of these subjects are expected to be eligible to receive RNS60 per study protocol. RNS60 will be administered in two ways: by IV infusion one day a week (infusions to occur at MGH) and by inhalation (once a day for the remaining 6 days a week). All visit windows (\pm 3 days) are consecutive calendar days and are calculated from the day the participant starts study treatment (the day of the Baseline Visit).

4.2 Study Centers

This study will be conducted as a single center study at the MGH.

4.3 Study Duration

Subjects in the core study will remain on treatment for 24 weeks. Subjects may elect to continue with the 24-week extension phase sometime between Week 18 and Week 23. Each subject will also have a Follow-up Telephone Interview 28 days \pm 5 to assess for AEs, changes in concomitant medications and to administer the ALSFRS-R.

4.4 Protocol Adherence

The Principal Investigators (PIs) agree to adhere to the protocol detailed in this document and agrees that any changes to the protocol must be approved by the site Institutional Review Board (IRB). The PIs will be responsible for enrolling only those study subjects who have met protocol eligibility criteria.

5 SELECTION AND WITHDRAWAL OF STUDY POPULATION

5.1 Number of Study Subjects

Approximately 25 subjects will be consented for the study. Any subject who signs consent will be considered enrolled in the study. Screening study procedures will begin after informed consent.

If a subject fails screening, at a minimum, the following information will be captured and entered in the data capture system: inclusion/exclusion criteria, demographics, screening lab results, reason for screen failure.

Fifteen (15) subjects will receive RNS60 for up to 48 weeks per study protocol and will be followed up to 52 weeks.

5.2 Inclusion and Exclusion Criteria

5.2.1 Inclusion Criteria

Study subjects meeting all of the following criteria will be allowed to enroll in the study:

- 1- ALS volunteers must be diagnosed as having possible, probable, probable-laboratory supported, or definite ALS, either sporadic or familial according to modified El Escorial criteria.
- 2- Age 18-80, able to provide informed consent, and comply with study procedures.
- 3- Participants must not have taken riluzole for at least 30 days, or be on a stable dose of riluzole for at least 30 days, prior to screening (riluzole-naïve participants are permitted in the study).
- 4- Women must not be lactating or able to become pregnant (e.g. post menopausal, surgically sterile, or using adequate birth control) for the duration of the study and 3 months after study completion.
- 5- Males should practice contraception for the duration of the study and 3 months after completion.

Study subjects in the “Imaging group” will also need to meet the following additional inclusion criteria:

- 1- Ability to safely lie flat for 90 min for PET procedures in the opinion of the study physician.
- 2- High or mixed affinity to bind TSPO protein (Ala/Ala or Ala/Thr) (Details below).
- 3- Score of 25 or greater (out of 45) on the Upper Motor Neuron Burden (Details below).

TSPO affinity test: venous blood will be drawn from all participants at Screening in order to have them genotyped for the Ala147Thr TSPO polymorphism in the *TSPO* gene (rs6971). About 10% of humans show low binding affinity to PBR28²⁴. A recent study has demonstrated that the rs6971 polymorphism predicts PBR28 binding affinity in human platelets²⁵. Since the low-affinity binder phenotype is consistent across all tissues within the same person, testing for the Ala147Thr polymorphism can be performed to predict low affinity for PBR28 in all organs, including the brain²⁵. High or Mixed affinity binders (Ala/Ala or Ala/Thr) will be considered eligible, whereas the low affinity binders (Thr/Thr) will be considered ineligible for the study.

Upper Motor Neuron Burden (UMN-B): The UMN-B at screening will be calculated by assessing five bilateral deep tendon reflexes on a scale of 0-4, as well as three pathological reflexes (bilateral Hoffman and Babinski signs, and jaw jerk) 0 or 1, for a total possible score of 45. Subjects screening for the imaging group with scores of 25 or more may be considered eligible.

5.2.2 Subject Exclusion Criteria

Study subjects meeting any of the following criteria during screening evaluations will be excluded from entry into the study:

- 1- Abnormal liver function defined as AST and/or ALT > 3 times the upper limit of the normal.
- 2- Renal insufficiency as defined by a serum creatinine > 1.5 times the upper limit of normal.
- 3- The presence of unstable psychiatric disease, cognitive impairment, or dementia that would impair ability of the participant to provide informed consent, according to PI judgment.
- 4- Clinically significant unstable medical condition (other than ALS) that would pose a risk to the participant if they were to participate in the study.
- 5- History of HIV, clinically significant chronic hepatitis, or other active infection.
- 6- Active participation in another ALS clinical trial within 30 days of the Screening Visit

Study subjects in the Imaging group meeting any of the additional following criteria during screening evaluations will be excluded from entry into the study:

- 1- Exposure to immunomodulatory medications within 30 days of the Screening Visit.
- 2- Any contraindication to undergo MRI studies such as
 - a. History of a cardiac pacemaker or pacemaker wires
 - b. Metallic particles in the body
 - c. Vascular clips in the head
 - d. Prosthetic heart valves
 - e. Claustrophobia
- 3- Radiation exposure that exceeds the site's current guidelines

- 4- Current use of tobacco products including cigarettes, cigars, snuff and chewing tobacco, or nicotine replacement products such as gum or patch.
- 5- Current use of medications / treatments under investigation in ALS clinical trials or use of “off-label” medications for ALS as determined by the clinical judgment of the principal investigator.

5.3 Withdrawal

A study subject will be discontinued from participation in the study if:

- Any clinical AE, laboratory abnormality, concurrent illness, or other medical condition or situation occurs such that continued participation in the study would not be in the best interest of the subject.
- The participant meets any exclusion criteria (either newly developed or not previously recognized).

Subjects are free to withdraw from participation in the study at any time upon request.

5.3.1 Handling of Withdrawals

A subject may choose to discontinue participation in the study at any time. Subjects who permanently discontinue study drug should complete early study drug termination procedures per protocol. The subject should then return any unused study drug and will be asked to return to the study site for a final safety visit. At that visit, the subject will be asked to have a final telephone call 28 days (+ 5 days) after taking their last dose of study drug.

5.3.2 Termination of Study

This study may be prematurely terminated if, in the opinion of the PIs, there is sufficient reasonable cause.

Circumstances that may warrant termination include, but are not limited to:

- Determination of unexpected, significant, or unacceptable risk to subjects.
- Enrollment is unsatisfactory.
- Insufficient adherence to protocol requirements.
- Data are not sufficiently complete and/or evaluable.

6 TREATMENTS ADMINISTERED

6.1 Treatments

6.1.1 Study Product Description

[REDACTED]

[REDACTED]

[REDACTED]

[REDACTED]

6.1.2 Treatments administered

RNS60 will be administered in two ways: by IV infusion one day a week (infusion dose: 375 ml, infused over a 40-minute period) and by inhalation (the remaining 6 days a week, 4 ml/day). The nebulizer system supplied is comprised of the PARI Trek S nebulizer compressor and the LC Sprint reusable nebulizer.

[REDACTED]

RNS60 will be administered intravenously at weekly study visits (starting on the Baseline visit) at the clinic site by properly trained staff designated by the investigator. Subjects will receive 375 ml RNS60 infused over 40 minutes. Infusion documentation should include recording infusion start and stop times, volume infused, and any interruptions to the infusion.

During the remaining days of the week, treatment with RNS60 will be nebulized at home in the morning.

6.2 Receiving, Storage, Dispensing

6.2.1 Receipt of Drug Supply

RNS60 will be provided by Revalesio Corporation (Tacoma, WA). The company will supply both the IV and inhalation preparations. RNS60 will be shipped directly to the MGH Research Pharmacy. The Research Pharmacist will be responsible for keeping records of study drug receipt and inventory.

6.2.2 Storage

The drug supply will be kept refrigerated in the MGH Research Pharmacy with access limited to those directly involved in the study.

6.2.3 Dispensing of Study Drug

[REDACTED]

[REDACTED]

6.3 Modification of Study Intervention/Investigational Product for a Subject

Any dosage adjustment, including the reason for and dates of adjustment, will be documented in the CRF for each subject requiring this manipulation. The PIs or licensed physician Sub-Investigator may reduce the dosage of study drug or discontinue the study drug in its entirety for AEs thought to be related to the study drug or for other reason during the trial (the reason for, and dates of suspension or dose reduction must be documented). If the AE is mild or moderate, the dosage may be reduced until the event improves. The PIs may then choose to resume the higher dosage or maintain the subject at a reduced dosage. The option to continue with administration by IV only or inhalation only is allowable.

If the event is serious or life threatening, and deemed to be definitely drug related, the study drug will be discontinued immediately. Study subjects must remain off the study drug permanently. Subjects may not resume study drug. All AEs will be followed to resolution.

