6.3.1. Dosage Discontinuation

Reasons for discontinuation of study medication may include an AE, PI recommendation, protocol deviation, loss-to-follow-up, patient request, or patient death.

Study subjects who discontinue study drug prematurely (early termination from study) will be encouraged to return for a Final Safety Visit and participate in a Follow-Up Telephone Call 28 days (+ 5 days) after the last dose of study drug.

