6.7 Statistical considerations

Sample size calculation was based on the primary outcomes of safety and tolerability. With a sample size of 15 participants, we will have over a 90% chance of seeing at least one occurrence of any adverse event whose probability of occurrence is 15% or greater. Tolerability will be defined as the ability of subjects to complete the entire 24-week treatment portion of study. With 15 participants on active drug in this study, if 10 or more participants tolerate the drug, there is an 85% chance that the true tolerability among people with ALS is at least 75%. Furthermore, if 10 or more people tolerate the drug, there is only a 3% chance that the true tolerability will be as low as 40% in people with ALS. For people in the Biomarker group, primary outcomes will include changes in the ROI in the motor cortex as assessed by [11C]-PBR29-PET. Our previous studies comparing mean PBR28 binding in the motor cortices in limb-onset ALS subjects (1.18 units) with matching healthy volunteers (1.064 units) revealed 0.116 mean difference between the two groups, with 0.08 standard deviation in the ALS group. With 10 people in the Biomarker group, the probability is 90 percent that the study will detect a treatment difference at a one-sided 0.1 significance level if the true difference is 0.096 units.

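### Tolerability counts anyone who finishes 24 weeks, including on one route or a reduced dose, and no completion rate for the planned two-route regimen is set beside it

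*Combined protocol and SAP*

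**What the plan says.** Section 6.1.2 sets a two-route regimen: 375 ml by infusion once a week and 4 ml by inhalation on each of the other six days.

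Section 3.2 lists as a primary outcome "Tolerability, defined as the ability of subjects to complete the entire 24-week treatment portion of study". Section 6.7 repeats the definition and bases the sample size on safety and tolerability. Neither section mentions dose or route.

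Section 6.3 allows the dose to be reduced or the drug stopped "for AEs thought to be related to the study drug or for other reason during the trial". After a reduction, "The PIs may then choose to resume the higher dosage or maintain the subject at a reduced dosage". It adds: "The option to continue with administration by IV only or inhalation only is allowable". It treats all of this as distinct from stopping the drug altogether. Section 6.3.1 links early termination to premature discontinuation of study drug and does not mention loss of a single route.

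The records are good. Under 6.3, "Any dosage adjustment, including the reason for and dates of adjustment, will be documented in the CRF for each subject requiring this manipulation". Under 6.1.2, "Infusion documentation should include recording infusion start and stop times, volume infused, and any interruptions to the infusion". Section 6.4 adds inhalation diaries and drug reconciliation, and 9.2.1 adds the action taken on study drug for each adverse event.

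The number treated is 18 in the Protocol Summary and 3.1 (approximately 18 in 4.1), but 15 in 5.1 and 6.7.

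Parts of 6.1.2 and all of 6.2.3 are redacted. Sections 3.2, 6.3 and 6.7, which govern this point, are readable.

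**The concern.** A subject who drops inhalation, or stays on a lower dose, because of an adverse event attributed to RNS60 has shown limited tolerance of the regimen under test. Under 3.2 and 6.7 the same subject adds one to the tolerability count. Someone who sees only the completion rate could take it as the share of patients able to sustain both routes, which is what the design of a later trial would need to know. The individual records would reveal such cases, but no readable section plans a summary that uses them.

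The statement in 6.7 that accompanies this outcome has a related weakness. It is calculated for 15 subjects although 18 are planned, and it does not say whether tolerating the drug means finishing on any regimen or on the planned one.

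**Working it through.** **Inputs.** From 6.7: n = 15, threshold 10, true rates 75% and 40%, stated chances 85% and 3%. From the Protocol Summary and 3.1: n = 18. The number of subjects who complete on a modified regimen is not in the documents, so it is left as m.

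**1. The plan's own figures.** With X binomial(n, p), P(X ≥ 10) is the sum over k = 10 to n of C(n,k) p^k (1−p)^(n−k).
- n = 15, p = 0.75: 0.852 (stated 85%).
- n = 15, p = 0.40: 0.034 (stated 3%).

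Both reproduce, but as the chance of the result given the true rate. Section 6.7 words them the other way round, as the chance of a true rate given the result.

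**2. How a modified-regimen completer is counted.** The subject stops inhalation for an adverse event, continues infusions as 6.3 allows, and reaches the end of treatment. The subject has not discontinued study drug, so 6.3.1 does not apply. The 24 weeks are complete, so 3.2 is met. A subject kept on a reduced dose is counted in the same way.

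**3. Size per subject.** Two-route completers are a subset of all completers. The any-regimen rate minus the two-route rate is therefore m/n, which is never negative.
- n = 18: 1/18 = 0.056, or 5.6 points per subject.
- n = 15: 1/15 = 0.067, or 6.7 points per subject.

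**4. Illustration.** Assume that 14 of 18 complete on any regimen. Intervals are exact (Clopper-Pearson) 95%.

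| m | Two-route completers | Rate | 95% CI |
|---|---|---|---|
| 0 | 14/18 | 0.778 | 0.524 to 0.936 |
| 1 | 13/18 | 0.722 | 0.465 to 0.903 |
| 2 | 12/18 | 0.667 | 0.410 to 0.867 |

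**5. What the 3% refers to.** Assume a true two-route rate of 40%, with a further share of all subjects completing on a modified regimen. The documents give no such share; the range 0% to 30% is an assumption. The chance of 10 or more completers among 15 is then:

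| Further share | P(X ≥ 10) |
|---|---|
| 0% | 0.034 |
| 5% | 0.077 |
| 10% | 0.151 |
| 20% | 0.403 |
| 30% | 0.722 |

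The 3% describes the two-route regimen only if nobody completes on a modified one.

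**6. Section 6.7 with 18 subjects.**

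| Threshold | As a proportion | P at true 75% | P at true 40% |
|---|---|---|---|
| 10 of 15 (as stated) | 67% | 0.852 | 0.034 |
| 10 of 18 | 56% | 0.981 | 0.135 |
| 12 of 18 | 67% | 0.861 | 0.020 |

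Keeping the threshold at 10 lowers the bar from 67% to 56%. Keeping the proportion nearly restores the stated properties.

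**The case against.** The strongest reply is that the plan never sets out to estimate tolerability of the two-route regimen as a separate quantity. Section 3.1 speaks of tolerability of RNS60, and 6.3 belongs to the same protocol, so finishing under its permitted changes is finishing treatment as planned. This stands. Any-regimen completion is a legitimate outcome for an open-label pilot, and 6.3 need not change. What remains is that the outcome does not say what it includes and has no two-route figure beside it.

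Three stronger readings are tempting, and the documents do not support them.

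- A reader might infer that the classification of modified-regimen completers is left open until results are seen. For the primary count it is not: as written, they count as completers. The word entire in the definition most naturally refers to the 24 weeks. If the full regimen was meant, the plan does not say so.
- A reader might infer that the completion rate overstates true drug tolerability overall. Section 6.3.1 also lists death, loss to follow-up, patient request and protocol deviation as reasons for stopping. These lower completion without necessarily showing intolerance, so the net direction is unknown.
- A reader might infer from 0.98 and 0.13 that the rule in 6.7 fails at 18 subjects. Those values come from holding the threshold at 10; 12 of 18 gives 0.86 and 0.02.

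It is also fair to say that the records allow a two-route rate to be derived later, that no decision is tied to the 10-of-15 statement, and that a shift of one subject is small beside the interval width at this sample size. These points limit the importance of the gap, but recording data is not the same as planning an analysis of them.

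**Conclusion.** The point holds in a limited form. The completion rate is at or above the two-route completion rate by construction, by 5.6 points per modified-regimen completer with 18 treated. The number of such subjects is unknown, so the total difference cannot be stated and may be zero. Neither an error in the primary definition nor a net overstatement of drug tolerability is shown. The gap is a missing statement of what the outcome includes and a missing companion rate.

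This rests on the readable text of 3.2, 6.3, 6.3.1 and 6.7. The illustration of 14 completers and the 0% to 30% range are assumptions. The mismatch between 15 and 18 in 6.7 follows directly from the documents, and that figure needs restating in any case.

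**What to change.** Leave 6.3 as it is and keep any-regimen completion as the primary tolerability outcome.

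1. In 3.2 and 6.7, state that it includes one-route and reduced-dose completers.
2. Pre-specify beside it, with an exact 95% CI, the proportion of treated subjects who complete 24 weeks on both routes with no route drop or dose reduction for an adverse event rated possibly, probably or definitely related to RNS60 (9.2.2). Relatedness is needed because 9.1.1 records ALS progression as an adverse event.
3. Exempt only a temporary change reversed within a short period stated in advance, for example 4 weeks. A rule that looks only at the end of treatment would count as fully tolerant a subject who spent months on one route and resumed late.
4. List changes for other reasons, including ALS progression, separately, and state in advance how a lasting route drop for such a reason is handled in the two-route rate. Stopping the nebulizer because of disease progression should not be read as drug intolerance.
5. Restate 6.7 for 18 subjects, say which outcome it refers to, and word the probabilities as the chance of the result given the true rate. A threshold of 12 of 18 keeps the stated properties nearly unchanged.

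The cost is a few sentences in 3.2 and 6.7 and one more table. No new data, added patient burden or change in sample size is needed. The downsides are a supplementary rate that may be lower than the primary one, and reliance on the recorded reason and relatedness of each change.
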